Preterm neonates between 26 and 28 completed weeks PMA who are within the first 20 hours after birth and who had successful implementation of controlled nCPAP within 90 minutes of birth will be considered to be potential subjects. Before study enrollment, legal guardians will provide a written informed consent form (ICF) for each potential subject. Qualification for study enrollment will be established after confirmation that the subject has met all of the inclusion criteria and none of the exclusion criteria. The clinical criteria for enrollment may be met prior to informed consent being obtained; however, no study-specific procedures that are not part of the usual standard care of the subject at the institution may be performed until the informed consent has been provided by a legally authorized representative of the subject. Inclusion criteria to be met within the first 20 hours after birth includes a required nCPAP of 5 to 6 cm H₂O to maintain SpO₂ of 88% to 95% with a fraction of inspired oxygen (FiO₂) within a range of 0.25 to 0.50 for at least 30 minutes. As soon as study eligibility has been confirmed and the informed consent is signed, subjects will be randomized to either an active arm or a control arm. Subjects randomized to an active arm will receive 1 dose of lucinactant for inhalation within 2 hours of randomization; subjects must continue to meet entry criteria at the time of initiation of study therapy. Active study therapy will be administered through the investigational ADS device over 30, 45, 60, or 90 minutes in conjunction with nCPAP support.

Subjects may be eligible to receive a repeat dose between 2 and 24 hours after the initial dose if subjects meet repeat dosing criteria, as

described in the “Treatment Groups” section. Subjects randomized to a control arm will be continued on nCPAP alone.

A safety assessment will be performed by an independent SRC after each group has been enrolled. All subjects on the active arm will receive the same drug concentration of lucinactant for inhalation at the same rate. The dose will vary by the volume of the nominal dose of lucinactant (30 mg TPL/ml) aerosolized and introduced into the nCPAP circuit, given over a predetermined time for each dose. The lucinactant for inhalation delivery will be facilitated by the investigational ADS device in conjunction with a commercially available nCPAP generator and patient interface.

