Control Arm (n = 8): Continuous nCPAP

Each dosing group will complete study dosing and all active subjects will complete 72 hour safety assessments and procedures before the SRC review. The SRC will review all available safety data (to include study-related adverse events [AEs], including adverse device effects [ADEs], serious adverse events [SAEs], and additional safety endpoints). Enrollment will continue in the next dosing group without pause from the previous dosing group; however, if the SRC identifies safety concerns that would preclude dosing, enrollment will stop until these safety concerns are addressed and the SRC recommends resuming enrollment.

Repeat dosing will be allowed in each dosing group. Subjects meeting the repeat dosing criterion will receive an additional treatment of the same dose. Repeat dosing will be allowed between 2 hours and 24 hours after completion of the initial dose if subjects require a sustained need for supplemental oxygen at or above the qualifying FiO₂ level for study entry (ie, 0.25) for at least 30 minutes to maintain SpO₂ of 88% to 95%.

Subjects will be followed for safety evaluations (including, but not limited to, AEs and concomitant medications) until the subject is

36 weeks PMA or is discharged. A final visit will occur at 36 weeks PMA or at the time of discharge or withdrawal (whichever occurs first) for all subjects.

Inclusion Criteria:

1. Signed ICF from legally authorized representative;
2. Gestational age 26 to 28 completed weeks PMA;
3. Successful implementation of controlled nCPAP within 90 minutes after birth;
4. Spontaneous breathing;
5. Chest radiograph consistent with RDS;
6. Within the first 20 hours after birth, requires an nCPAP of 5 to 6 cm H₂O to maintain SpO₂ of 88% to 95% with an FiO₂ of 0.25 to 0.50 that is clinically indicated for at least 30 minutes. Transient (<10 minutes) FiO₂ excursions below 0.25 or above 0.50 do not reset the 30 minute requirement.

Exclusion Criteria:

1. Heart rate that cannot be stabilized above 100 beats per minutes within 5 minutes of birth;
2. Recurrent episodes of apnea occurring after the initial newborn resuscitation period (ie, 10 minutes after birth) requiring intermittent positive pressure breaths using inflating pressures above the set CPAP pressure administered manually or mechanically through any patient interface;
3. A 5 minute Apgar score < 5;

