5.2.4 Sequential Dosing Scheme

The study dosing will initiate in Dosing Group I (the lowest dose), and continue to Dosing Group II after completion of enrollment. Each dosing group will enroll sequentially following completed enrollment of the previous dosing group. After all active subjects within each dosing group have completed 72 hours, the SRC will review the safety and tolerability of this dose.

If there appears to be intolerability with a given dose or operational challenges administering a dose, the remaining subjects may have the dose decreased to a previously administered dose, after consultation with the SRC.

Further details on the dosing for each dosing group are provided in Section 5.2.2.

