6.2 Safety Enrollment Holds

Failed tolerability will be established based on analysis of AEs. In particular, AEs related to the administration of lucinactant for inhalation are of particular interest. To prevent undue risk to subjects, if more than 2 subjects per dosing group experience an SAE related to dosing, enrollment and dosing will be suspended and further enrollment and dosing will proceed only if and when the SRC deems it to be appropriate.

In addition, if a treated subject dies during the first 12 hours following and related to lucinactant for inhalation administration, then an unscheduled meeting of the SRC will be called. Safety and

tolerability data will be presented to the SRC for their immediate review. Study enrollment will be suspended until such time that a safety assessment has been completed. Enrollment and dosing will proceed only if and when the SRC deems it to be appropriate. If the SRC deems it to be appropriate to re-initiate enrollment after an enrollment hold, IRB approvals will be obtained before the re-initiation of subject screening and enrollment activities.

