13.3 Sample Size and Randomization

Sample size is not based on statistical estimation for this phase 2 study. The number of subjects randomized (approximately 8 in each active group and approximately 8 in each control group) will be considered sufficient to establish safety and tolerability before proceeding to the next higher dose. The total of approximately 32 subjects assigned to the active arm and approximately 32 subjects for the control arm for the entire study is considered sufficient to assess overall safety and tolerability.

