Dosing Group I	Active Arm : 50 mg TPL/kg Delivered over 30 minutes in conjunction with nCPAP 1 repeat dose allowed if repeat dosing criterion met	n=8
	Control Arm : Continuous nCPAP	n=8
Dosing Group II	Active Arm : 75 mg TPL/kg Delivered over 45 minutes in conjunction with nCPAP 1 repeat dose allowed if repeat dosing criterion met	n=8
	Control Arm : Continuous nCPAP	n=8
Dosing Group III	Active Arm : 100 mg TPL/kg Delivered over 60 minutes in conjunction with nCPAP 1 repeat dose allowed if repeat dosing criterion met	n=8
	Control Arm : Continuous nCPAP	n=8
Dosing Group IV	Active Arm : 150 mg TPL/kg Delivered over 90 minutes in conjunction with nCPAP 1 repeat dose allowed if repeat dosing criterion met	n=8
	Control Arm : Continuous nCPAP	n=8

Note: TPL = Total Phospholipids

Dosing Group I will complete study dosing and all active subjects will complete 72 hour safety assessments and procedures before the Safety Review Committee (SRC) review. The SRC will complete their review of all available Dosing Group I safety data (to include study-related adverse events [AEs], serious adverse events [SAEs], and additional safety endpoints) before recommending advancing enrollment to additional dosing groups. If the SRC concludes there are no safety concerns that would preclude proceeding to the next higher dose, dosing will commence in Dosing Group II. Likewise, the SRC will review the safety and tolerability of this dose and each succeeding dose, with dosing proceeding in the next dosing group if the SRC determines there are no safety concerns.

Repeat dosing will be allowed in each dosing group. Subjects meeting the repeat dosing criterion will receive an additional treatment of the same dose. Repeat dosing will be allowed between 2 and 24 hours after completion of the initial dose.

Subjects will be followed for safety evaluations (including, but not limited to, AEs and concomitant medications) until the subject is 36 weeks PMA or is discharged. Descriptive statistics (number of subjects, percent, mean, standard deviation, median, minimum, maximum) will be presented by treatment group, defined as each of the active doses (n = 8; 32 subjects total) and the all controls combined (n = 32). A final visit will occur at 36 weeks PMA or at the time of discharge or withdrawal (whichever occurs first) for all subjects.

Key safety and tolerability endpoints in the study include:

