2.2.1 Treatment Groups

Study Group	Treatment Assignment	Number of Subjects
Dosing Group I	Active Arm : 50 mg TPL/kg Delivered over 30 minutes in conjunction with nCPAP 1 repeat dose allowed if repeat dosing criterion met	n=8
	Control Arm : Continuous nCPAP	n=8
Dosing Group II	Active Arm : 75 mg TPL/kg Delivered over 45 minutes in conjunction with nCPAP 1 repeat dose allowed if repeat dosing criterion met	n=8
	Control Arm : Continuous nCPAP	n=8
Dosing Group III	Active Arm : 100 mg TPL/kg Delivered over 60 minutes in conjunction with nCPAP 1 repeat dose allowed if repeat dosing criterion met	n=8
	Control Arm : Continuous nCPAP	n=8
Dosing Group IV	Active Arm : 150 mg TPL/kg Delivered over 90 minutes in conjunction with nCPAP 1 repeat dose allowed if repeat dosing criterion met	n=8
	Control Arm : Continuous nCPAP	n=8

Note: TPL = Total Phospholipids

The study dosing will initiate in Dosing Group I at the lowest dose. Only after completion of the Safety Review Committee (SRC) review and subsequent approval, will the study progress to the next dose level for subjects in Dosing Group II. After all active subjects within each dosing group have completed assessments through 72 hours; the SRC will review the safety and tolerability of this dose. Following enrollment completion and SRC approval, dose escalation will proceed to the next dosing group.

If there appears to be intolerability with a given dose or operational challenges administering a dose, the remaining subjects may have the dose decreased to a previously administered dose, after consultation with the SRC.

The term “treatment group” will be defined as subjects in each of the active doses and the control arm subjects combined.

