7.2 INTERIM ANALYSES

Four interim analyses are planned. Each interim analysis will occur when all subjects from each dosing group have been enrolled and all active subjects have completed 72 hours. In addition to the planned analyses, if more than 2 subjects in any dosing group experience an SAE related to dosing, aerosol delivery will be suspended and further dosing will proceed only if and when the SRC deems it to be appropriate.

In addition, if a treated subject dies due to a related event during or within 12 hours after aerosol administration, then an unscheduled meeting of the SRC will be called. Safety and tolerability data will be presented to the SRC for their immediate review. Study enrollment will be suspended until such time that a safety assessment has been completed and dosing will proceed only if and when the SRC deems it to be appropriate. If the SRC deems it to be appropriate to re-initiate enrollment after an enrollment hold, local IRB approvals will be obtained before the re-initiation of subject screening and enrollment activities. The objective of the interim analyses is to ensure the safety of subjects at a particular dose before proceeding to the next higher dose.

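### Protocol and SAP give incompatible dose-escalation rules: the protocol opens the next dose without waiting for the SRC, the SAP only after SRC review and approval

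*Protocol*

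**What the plan says.** **Escalation, protocol.** The Study Design part of the summary states "A safety assessment will be performed by an independent SRC after each group has been enrolled". The Dosing Groups part then has enrolment move on directly: "next dosing group without pause from the previous dosing group; however, if the SRC identifies safety concerns that would preclude dosing, enrollment will stop". It restarts when those concerns have been dealt with and the SRC advises it. Section 5.2.4 is in line with this: "Each dosing group will enroll sequentially following completed enrollment of the previous dosing group". It places the SRC review after all active infants in the group have completed 72 hours and names no approval step.

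**Escalation, SAP.** The Executive Summary makes the SRC's conclusion the trigger: "If the SRC concludes there are no safety concerns that would preclude proceeding to the next higher dose, dosing will commence in Dosing Group II". It applies the same order to each later dose. Section 2.2.1 is stricter: "Only after completion of the Safety Review Committee (SRC) review and subsequent approval, will the study progress to the next dose level". It then requires SRC approval, as well as completed enrolment, for each further step.

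**Stated purpose.** SAP 7.2 says the interim analyses are there to "ensure the safety of subjects at a particular dose before proceeding to the next higher dose". Protocol 13.3 says that about 8 infants per arm in each group is "considered sufficient to establish safety and tolerability before proceeding to the next higher dose".

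**Repeat dose.** The protocol (summary and 5.2.5) requires a need for FiO2 at or above 0.25, sustained for at least 30 minutes, to hold SpO2 at 88% to 95%. SAP 2.2.2 requires an FiO2 of at least 0.35 and sets no duration or SpO2 condition. Both use the window of 2 to 24 hours.

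**The concern.** In a sequential dose-escalation trial, the order of review and escalation is the central safety step. Under the protocol, the SRC review is a chance to stop a dose that may already be open. Under the SAP, it is a condition for opening that dose. SRC members and the independent statistician could read their role either way, depending on which document they hold.

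Sites dose under the protocol, and SAP section 1 says the SAP only adds detail to analyses outlined there. The likelier result is therefore an SAP that describes a different trial from the one run. Protocol 13.3 would also claim an ordering, safety established first and the higher dose afterwards, that the protocol's own enrolment rule does not guarantee.

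The repeat-dose mismatch matters less. The two documents define eligibility differently, but the SAP summarises only the number of doses received (3.3.2) and the number of infants given a repeat dose (6.3), so no planned output changes.

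**Working it through.** **1. The two rules side by side**

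| Question | Protocol | SAP |
|---|---|---|
| When does the SRC review? | All active infants at 72 h (5.2.4, 6) | All active infants at 72 h (2.2.1, 7.2) |
| What opens the next dose? | Completed enrolment of the current group (summary, 5.2.4) | Completed enrolment and SRC approval (Executive Summary, 2.2.1) |
| What does the SRC do? | Stops enrolment if it sees a concern | Must approve first |
| Can an infant get the next dose before the review? | Yes | No |

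The last row is a direct contradiction. The plan gives no figure to reproduce here, because it has no hypothesis test and no statistical sample size.

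**2. How far apart the rules are in practice (illustration)**

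Inputs from the documents:
- 16 infants per group, 8 active and 8 control (protocol 5.2.2), in blocks of 4 (5.2.3).
- Accrual, first reading: 64 infants in 7 months. 7 months = 30.44 weeks, and 64 / 30.44 = 2.10 per week (summary).
- Accrual, second reading: 12 sites at 1 infant per 4 weeks = 3.0 per week (2.3). The readings disagree, since 3.0 × 30.44 = 91 infants, not 64.
- Accrual, third reading: about 25 sites (4.1) at the same per-site rate = 6.25 per week.

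Assumptions: SRC turnaround W of 0, 1, 2 or 4 weeks after the 72 h point (not stated in the documents), Poisson arrivals and 2:2 blocks.

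The 72 h clock starts at the last active infant of the group. In 2:2 blocks this is the 16th, 15th or 14th infant enrolled, with probability 1/2, 1/3 and 1/6. On average 0 × 1/2 + 1 × 1/3 + 2 × 1/6 = 0.67 control infants are still to be enrolled in that group. As a hand approximation, the active infants at the next dose before review number

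½ × [rate × (3/7 + W) − 0.67], with a maximum of 8.

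At 2.10 per week:
- W = 1: ½ × (3.00 − 0.67) = 1.17
- W = 2: ½ × (5.11 − 0.67) = 2.22
- W = 4: ½ × (9.31 − 0.67) = 4.32

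Simulation (400,000 runs per rate), which handles the limits at 0 and 8 exactly:

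| Rate per week | W (weeks) | Mean active infants before review | 95th percentile | Chance of at least one |
|---|---|---|---|---|
| 2.10 | 0 | 0.28 | 1 | 0.24 |
| 2.10 | 1 | 1.2 | 3 | 0.71 |
| 2.10 | 2 | 2.2 | 4 | 0.91 |
| 2.10 | 4 | 4.3 | 7 | >0.99 |
| 3.0 | 0 | 0.43 | 2 | 0.35 |
| 3.0 | 1 | 1.8 | 4 | 0.86 |
| 3.0 | 2 | 3.3 | 6 | 0.98 |
| 3.0 | 4 | 6.1 | 8 | >0.99 |

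At 6.25 per week the means for W = 1, 2 and 4 are about 4.1, 6.8 and 8.0. Under the SAP rule every entry is 0. The figures are per step, and there are three steps.

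**3. Time cost if enrolment waits for the SRC**

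The wait at each step is the time from the 16th enrolment to the SRC report (last active infant + 3/7 week + W), not below 0. Three times the mean wait is 3.4, 6.3 or 12.3 weeks at 2.10 per week for W = 1, 2 or 4, and 3.6, 6.6 or 12.6 weeks at 3.0 per week.

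**The case against.** **The protocol governs, and its hold rules protect infants under either version.** Section 6.2 provides that "if more than 2 subjects per dosing group experience an SAE related to dosing, enrollment and dosing will be suspended", and a related death within 12 hours of dosing also triggers a hold. SAP 7.2 carries both triggers. This is true, and it limits the practical harm. But the holds respond to events once they have occurred. They do not say whether the scheduled review must precede the next dose, and they leave the SAP text wrong.

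**The no-pause rule has thin support.** Only one sentence, in the summary, states it outright. The Study Design sentence fits both rules, and section 5.2.4 supports no-pause only by naming no approval step. Section 6.1 lists continuing at the next higher dose level among the SRC's possible recommendations, which can be read as a decision to escalate. This stands, and it means section 6.1 belongs in the reconciliation. It does not remove the conflict, because the summary sentence is current text and contradicts SAP 2.2.1.

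**Protocol 13.3 is only a sample-size rationale.** It sets no review timing, so it is weaker evidence than SAP 2.2.1. It still asserts an ordering that the enrolment rule does not secure.

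**The numbers rest on an assumed turnaround.** They do. With zero turnaround the mean falls to 0.28 at 2.1 per week, and with 25 sites it rises to as much as 8. The contradiction is textual and needs none of these figures.

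**Conclusion.** The concern holds. The protocol and the SAP state escalation rules that cannot both be followed, and the repeat-dose criteria also conflict. Neither conflict depends on a calculation.

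How far the escalation rules diverge in practice depends on SRC turnaround and accrual. For 1 to 4 weeks' turnaround, the mean is about 1.2 to 4.3 of 8 active infants per step at 2.1 per week, or 1.8 to 6.1 at 3.0 per week. It is smaller if the SRC reports at once and larger if 25 sites recruit at the planned per-site rate. These figures measure the gap between the rules and do not favour either.

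This should be fixed, but it does not stop the trial from operating: sites have a workable rule in the protocol, the holds apply either way, and no hypothesis test is affected. The repeat-dose mismatch is secondary.

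**What to change.** The sponsor and the SRC should decide on one escalation rule and one repeat-dose criterion, then make every affected section say the same thing.

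- **If the next dose may open before the review:** correct the SAP Executive Summary and 2.2.1. Reword SAP 7.2 and protocol 13.3 so that they no longer say safety is ensured or established before the next dose.
- **If the review must come first:** change the Dosing Groups text of the protocol summary and section 5.2.4. The SAP text and protocol 13.3 can stay.
- **In either case:** make protocol 6.1 state whether the SRC's recommendation is a condition for the next dose or a chance to stop it.
- **Repeat dose:** reconcile the protocol summary and 5.2.5 with SAP 2.2.2, covering the FiO2 level, the duration and the SpO2 condition.

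Cost: the SAP edits are text corrections. Any protocol change, including to 13.3 or 6.1, needs an amendment with prior IRB approval (protocol 15.1). If enrolment is to wait for the SRC, it lengthens by a mean of about 3.4 to 12.6 weeks over three steps, for an assumed turnaround of 1 to 4 weeks and 2.1 to 3.0 infants per week.

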Appendix 5	International Classification of Retinopathy of Prematurity (ROP).....	101
Appendix 6	Investigator Agreement Form	102

LIST OF ABBREVIATIONS

Abbreviation	Description
ABG	Arterial blood gas
ACU	Aerosurf Control Unit
AE	Adverse event
ADE	Adverse device effect
ADS	Aerosurf Delivery System
ADP	Aerosurf Delivery Packet
BPD	Bronchopulmonary dysplasia
CAG	Capillary aerosol generator
CFR	Code of Federal Regulations
CPAP/nCPAP	Continuous positive airway pressure/nasal CPAP
CRF/eCRF	Case report form/electronic CRF
DPPC	dipalmitoylphosphatidylcholine
FDA	Food and Drug Administration
FiO₂	Fraction of inspired oxygen
GA	Gestational age
GCP	Good Clinical Practice
HIPAA	Health Insurance Portability and Accountability Act of 1996
ICF	Informed consent form
ICH	International Conference on Harmonization
IEC/IRB/REB	Independent Ethics Committee/Institutional Review Board/ Research Ethics Board
IMV	Intermittent mechanical ventilation
IND	Investigational new drug
IPP	Intermittent positive pressure
ITT	Intent-to-Treat
IVH	Intraventricular hemorrhage
IWRS	Interactive web response system

Abbreviation	Description
KL₄	21-amino acid hydrophobic synthetic peptide, also known as sinapultide
MMAD	Mass median aerodynamic diameter
NDA	New drug application
NEC	Necrotizing enterocolitis
NICU	Neonatal intensive care unit
NOEL	No observed adverse effect level
PA	Palmitic acid
PCO₂	Partial pressure of carbon dioxide
PaO₂	Partial pressure of oxygen dissolved in arterial blood
PDA	Patent ductus arteriosus
PI	Principal Investigator
PIF	Peak inspiratory flow
PMA	Post-menstrual age
POPG, Na	Palmitoyl-oleoyl-phosphatidylglycerol, sodium salt
PROM	Premature rupture of membranes
PVL	Periventricular leukomalacia
RDS	Respiratory distress syndrome
ROP	Retinopathy of prematurity
SAE	Serious adverse event
SIV	Site initiation visit
SpO₂	Oxygen saturation measured by pulse oximetry
SRC	Safety review committee
SRT	Surfactant replacement therapy
TORCH	Toxoplasmosis, rubella, cytomegalovirus, herpes simplex
TPL	Total phospholipids
UADE	Unanticipated adverse device effect
US	United States
V_m	Minute ventilation
WMA	World Medical Assembly

